### **3.4.3. Vital Signs**

Summary statistics for actual values and change from baseline will be tabulated for vital signs by treatment period, treatment group and scheduled visit.

### **3.4.4. Electrocardiogram**

The ECG parameters (heart rate, PR interval, QRS interval, QT interval, and QTc interval) at each time point as well as the change from baseline will be summarized with descriptive statistics by treatment period, treatment group, and scheduled visit. These parameters will be determined electronically by the ECG machine at the clinical site. QTc interval will be calculated using Fridericia's formula and will be categorized into the following groups:  $\leq 450$ ,  $> 450 - 480$ ,  $> 480 - 500$  and  $> 500$  ms. Categorized QTc interval will be summarized with frequency and percentage by treatment period, treatment group, and scheduled visit. Shift tables comparing the baseline categorized QTc interval to the maximum post-baseline categorized QTc interval will be provided by treatment period and treatment group. In addition, increase of  $> 30$  ms and  $> 60$  ms from baseline in QTc interval will be summarized with frequency and percentage by treatment period, treatment group, and scheduled visit.

The overall ECG assessment will be reported as "Normal," or "Abnormal – not clinically significant" or "Abnormal – clinically significant" with respect to relevant abnormalities by the investigator. Shifts from the baseline ECG assessment to the worst post-baseline ECG assessment will be tabulated by treatment period and treatment group.

## **4. PROTOCOL AND SAP AMENDMENTS**

Protocol Amendment 01 states that the p-value for the primary endpoint will be calculated by comparing to the effect size of -0.246. This effect size was estimated from the Inker's equation for the sample size calculation only. The SAP has clarified that the primary treatment comparison using the primary endpoint will be based on the two-sided p-value for the treatment difference in LS means at Week 36 (Section 2.9.2.1).

Protocol Amendment 02 was not released due to formatting errors identified after it was finalized. The formatting errors were corrected in Amendment A03.

Protocol Amendment 03 added criteria for re-initiation of study treatment and modifications to study procedures during the COVID-19 pandemic. Sensitivity analyses have been added to the SAP by excluding the data collected after the re-initiation of study treatment (Section 2.9.2).

Protocol Amendment 04 (soon to be released) adds new prohibited medications (SGL2Ti, Tarpeyo, Kerendia).

Protocol Amendment 05 will make the following major changes:

- The proteinuria responder analysis has been removed. Instead, UPE will be examined as a continuous variable (change in log-transformed 24-hour UPE from baseline to 36 weeks).
- The primary endpoint – change from baseline in log-transformed 24-hour UPE in g/day at 36 weeks – will only include the subset of patients with high-risk proteinuria (UPE  $\geq$  2 g/day) at baseline. All patients (UPE  $>1$  g/day at baseline) will be examined for UPE change from baseline, but now as a secondary endpoint. Specifically, the amended protocol will assess change from baseline in the 24-hour UPE in patients with baseline UPE of  $\geq$  2 g/day, and the timing of analysis will remain unchanged at 36 weeks.
- In light of the new data published by Inker et al. [Inker 2021] regarding the relationship between treatment effects on annualized 2-year eGFR Rate of Change and treatment effects on mean change in proteinuria at 9 months, the duration of the study was changed from 3 years to 2 years post randomization
- Utilizing the IgAN database from the University of Leicester, UK, the sample size required to detect a difference of 3.48 and 2.45 mL/min in 2-year annualized eGFR Rate of Change between narsoplimab and placebo was determined to be 280 and 450 patients, respectively, for the high-risk proteinuria group (baseline UPE  $\geq$  2 g/day) and the all-patients population (UPE  $>1$  g/day), providing at least 85% power for a 2-sided test at 5% level of significance
- There were previously two sample size re-estimations (SSREs), one blinded SSRE for the UPE endpoint for all patients and the other for annualized eGFR rate of change endpoint. The former remained unchanged and was performed resulting in no change in the planned sample size of N = 280 for all patients. The latter has been removed in the proposed protocol amendment 05 and SAP, and has been replaced with a CP-based SSRE at the time of the primary UPE endpoint analysis in the high-risk proteinuria group (baseline UPE  $\geq$  2 g/day)

In reflection of these changes, the SAP was updated as follows:

- Data from [Inker 2021] regarding the relationship between treatment effects on 2-year annualized eGFR Rate of Decline and treatment effects on mean change in proteinuria at 9 months were added to the SAP
- Data from the University of Leicester IgAN database were used to estimate the annualized 2-year eGFR Rate of Decline for the placebo group with baseline proteinuria  $\geq$  2g/day. The sample size required to detect a difference of 3.48 mL/min in 2-year annualized eGFR Rate of Decline between narsoplimab and placebo in the

high-risk proteinuria group (baseline UPE  $\geq$  2g/day) patient population with at least 85% power for a 2-sided test at 5% level of significance, was determined to be 280 patients and this was added to the SAP

- Data from the University of Leicester IgAN database were used to estimate the annualized 2-year eGFR Rate of Decline for the all-patients placebo group with proteinuria  $> 1$  g/d. The sample size required to detect a difference of 2.45 mL/min in 2-year annualized eGFR Rate of Decline between narsoplimab and placebo in the all-patients population with 85% power at the 2-sided alpha level of 5% was determined to be 450 patients and this was added to the SAP
- Testing of hypotheses for primary UPE endpoint and key secondary eGFR endpoints was revised to be hierarchical in nature to control overall Type-1 error at 5%

## APPENDIX 1. JUMP TO PLACEBO MULTIPLE IMPUTATION

A control-based pattern-mixture model approach as per [Ratitch 2011] whereby missing observations in both the narsoplimab and placebo groups are imputed using only data observed in the placebo group; this model reflects a ‘jump to placebo (reference)’ analysis.

Several steps are required to execute this sensitivity analysis.

In the first step, intermittently missing data (e.g., where a patient has week 12 and week 36 data recorded but has week 24 data missing) are imputed as non-monotone missing to generate a monotone missing pattern. The form of the associated SAS code is given below where the dataset **DATAIN** has already been sorted by randomized treatment (**RANDTRT**) and the randomization stratification factors **STRAT1** and **STRAT2**:

```
/*FIRST STEP IMPUTE NON-MONOTONE (INTERMITTENTLY) MISSING DATA*/
PROC MI DATA=DATAIN SEED=<VALUE> NIMPUTE=20 OUT=MI_OUT1;
  VAR BASE W12 W24 W30 W36 ;
  MCMC CHAIN=MULTIPLE PRIOR=JEFFREYS IMPUTE=MONOTONE ;
  BY STRAT1 STRAT2 RANDTRT ;
RUN;
```

where **BASE** = baseline log UPE, and **W12**, **W24**, **W30** and **W36** = week 12, 24, 30 and 36 change from baseline log UPU values.

The resulting dataset **MI\_OUT1** is then sorted by **\_IMPUTATION\_**, **STRAT1**, **STRAT2** and **RANDTRT**. In the second step, **PROC MI** is called again utilizing the regression method under **MNAR** to complete imputation of the monotone missing datasets resulting from the first step. The SAS code will be of the following form:

```
/*SECONDLY IMPUTE MONOTONE MISSING DATA AS MNAR JUMP TO PLACEBO*/
PROC MI DATA=MI_OUT1 SEED = <SEED> NIMPUTE = 1 OUT=MI_OUT2;
  BY _IMPUTATION_ STRAT1 STRAT2 ;
  CLASS RANDTRT ;
  MONOTONE REG (W36 = BASE W12 W24 W30/ DETAILS) ;
  MNAR MODEL (W12 W24 W30 W36 / MODELOBS =(RANDTRT = 'PLACEBO')) ;
  VAR W12 W24 W30 W36 BASE ;
RUN;
```

The dataset **MI\_OUT2** contains the 20 complete imputed data sets. This dataset will be transformed in a third step such that, for each patient, each post-baseline time-point is represented by a separate record.

```
/*THIRD STEP TRANSFORM IMPUTED DATASETS*/
DATA MI_OUT3; SET MI_OUT2 ;
  VISIT=12; CHG_BL=W12-BASE; OUTPUT ;
  VISIT=24; CHG_BL=W24-BASE; OUTPUT ;
  VISIT=30; CHG_BL=W30-BASE; OUTPUT ;
  VISIT=36; CHG_BL=W36-BASE; OUTPUT ;
RUN;
```

The 20 complete datasets in **MI\_OUT3** will then be analyzed in a fourth step by MMRM via **PROC MIXED** as specified for the primary endpoint. The SAS code will be of the following form:

```
/*FOURTH STEP MMRM ANALYSIS OF IMPUTED DATASETS*/
PROC MIXED DATA=MI_OUT3 METHOD=REML;
  BY _IMPUTATION_;
  CLASS PATIENT RANDTRT VISIT STRAT1 STRAT2;
  MODEL CHG_BL = BASE RANDTRT VISIT RANDTRT*VISIT STRAT1 STRAT2
    STRAT1*STRAT2 /DDFM=KR;
  REPEATED VISIT / PATIENT = PATIENT TYPE = UN;
  LSMEANS RANDTRT*VISIT/SLICE=VISIT PDIFF DIFF ALPHA=0.05 CL;
  ODS OUTPUT DIFFS=DIFF LSMEANS=LSMEANS;
RUN;
```

To obtain overall LSmean and treatment effect estimates, the **DIFF** and **LSMEANS** datasets are merged in a fifth step prior to combination across imputations using Rubin's rule in a sixth step via **PROC MIANALYZE**. The SAS code will be of the following form:

```
/*FIFTH STEP MERGE DIFF AND LSMEANS DATASETS*/
DATA DIFF2;
  SET DIFF (IN=A) LSMEANS;
  IF A THEN COMPARISON=RANDTRT||' VS '||LEFT(_RANDTRT);
  ELSE COMPARISON=RANDTRT;
RUN;
PROC SORT DATA=DIFF2;
  BY COMPARISON _IMPUTATION_;
RUN;

/*SIXTH STEP COMBINE MI ESTIMATES VIA MERGE DIFF AND LSMEANS
  DATASETS*/
PROC MIANALYZE DATA=DIFF2;
  BY COMPARISON;
  MODELEFFECTS ESTIMATE;
  STDERR STDERR;
  ODS OUTPUT PARAMETERESTIMATES=MIESTS;
RUN;
```

The output dataset **MIESTS** contains the final, imputed results. The resulting multiply imputed means and difference in means between narsoplimab and placebo will be presented, along with the associated SEs, CIs and 2-sided p-values.

The same approach will be used for the analysis of the two key secondary endpoints, with **BASE** = baseline eGFR and log UPE change from baseline values at **W12**, **W24**, **W30** and **W36** replaced by absolute eGFR values at weeks **W12**, **W24**, **W36**, **W48**, **W60**, **W72**, **W84** and **W96**.

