### **2.9.2.1. Analysis of the Primary UPE Efficacy Endpoint in the High-Risk Proteinuria Group (Baseline UPE $\geq 2$ g/day)**

The primary efficacy endpoint will be based on the natural logarithm transformed 24-hour UPE. Descriptive statistics for the log-transformed 24-hour UPE change from baseline to 36 weeks, the geometric mean ratio (GMR) relative to the study baseline, and the coefficient of variation in percentage will be provided by treatment group for the FAS population.

The primary analysis will be a MMRM analysis on the change from baseline in log-transformed 24-hour UPE at Week 12, Week 24, Week 30, and Week 36. The model will be fitted in SAS via the PROC MIXED procedure. Terms will be included for treatment, time (as a categorical variable for the four timepoints), treatment by time interaction, and randomization strata as fixed effects. Within patient error will be modeled using an unstructured covariance matrix. Log baseline UPE will be included as a covariate in the model. Restricted maximum likelihood method will be used to estimate the model parameters. If the estimation of the model fails, an autoregressive (1) [AR(1)] covariance structure will be used. SAS code will be of the form,

```
PROC MIXED DATA=X METHOD=REML;
  CLASS PATIENT RANDTRT VISIT STRATA;
  MODEL CHG_BL = BASE RANDTRT VISIT RANDTRT*VISIT STRATA
    /DDFM=KR;
  REPEATED VISIT / PATIENT = PATIENT TYPE = UN;
  LSMEANS RANDTRT*VISIT/SLICE=VISIT PDIFF DIFF ALPHA=0.05 CL;
  ODS OUTPUT DIFFS=DIFF LSMEANS=LSMEANS;
RUN;
STRATA: Baseline eGFR level ( $\geq 30$  to  $\leq 45$  mL/min/1.73 m2 and  $> 45$  mL/min/1.73 m2)
```

The difference in least squares (LS) means at Week 36 between the treatment groups and its 95% confidence interval (CI) will be estimated. Two-sided p-value will be calculated. The LS mean at Week 36 will be estimated with 95% CI for each treatment group. The ratio of the GMR between the treatment groups will also be estimated with 95% CI.

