#### **Jump to Placebo Multiple Imputation**

The first approach will employ a control-based multiple imputation [Ratitch 2011] whereby missing observations in both the narsoplimab and placebo groups are imputed using only data observed in the placebo group; as such, this approach reflects a 'jump to placebo (or reference)' analysis. Imputation of values in the placebo arm will assume missing at random (MAR) while imputation of values in the narsoplimab arm will assume missing not at random (MNAR), i.e. as if the patient had been a member of the placebo arm. This approach does not assume a sustained benefit of narsoplimab treatment after discontinuation and limits a post-discontinuation effect to that of placebo. The approach will be implemented as follows:

- Step 1: Non-monotone missing data will be imputed first based on the MAR assumption and a multivariate joint Gaussian imputation model using Markov chain Monte Carlo (MCMC) method as per the MCMC statement in the SAS® PROC MI procedure. As a result, each imputed dataset will only have missing data at the end of patients' records, (a monotone missing data pattern). The MCMC method in the MI procedure will be used with multiple chains (option CHAIN=MULTIPLE), 100 burn-in iterations, and a non-informative prior. A separate imputation model will be used for each treatment arm. The imputation models will include the randomization stratification factors, baseline log UPE and change in log UPE at each time point. In case of non-convergence or non-estimability issues, a ridge prior and a single model will be considered with treatment arm added as explanatory variable to the model.
- Step 2: The remaining, monotone, missing data will be imputed using sequential regression multiple imputation model estimated based on data from the *placebo arm only*. Each sequential regression model (i.e., for imputation of values at a given time point) will include the stratification factors, baseline log UPE, and all previous values of UPE. Missing values at a given time point in placebo and narsoplimab treatment arms will be imputed from the same imputation model, conditional on patient values observed or imputed at previous time points.
- Step 3: The log change from baseline in UPE to each scheduled post-baseline visit will be calculated, based on observed and imputed data. Each of the imputed complete datasets from Step 2 will be analysed with the same MMRM model used for the primary analysis.

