- Step 4: The results of the analysis of each imputed dataset, i.e., treatment effect estimates and their standard errors, will be combined via the SAS® PROC MIANALYZE procedure using Rubin's rules [Rubin 1987] to produce an overall treatment effect estimate and its associated 95% confidence interval and 2-sided p-value.

Example SAS code of the form to perform this first sensitivity analysis is contained in [Appendix 1](#).

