## APPENDIX 2. TIPPING POINT MULTIPLE IMPUTATION

A tipping point analysis whereby missing data are imputed in the narsoplimab arm with an increasing degree of penalization and thus find the ‘tipping point’, i.e., that degree of penalization that renders a positive p-value for the primary endpoint non-significant.

All imputation steps are as described in [Appendix 1](#) apart from the second step where monotone missing data are imputed for patients randomized to narsoplimab are adjusted using the **ADJUST** and **SHIFT** options:

```
/*SECONDLY APPYING TIPPING POINT IMPUTATION*/
PROC MI DATA=MI_OUT1 SEED = <SEED> NIMPUTE = 1 OUT=MI_OUT2<DELTA>;
  BY_IMPUTATION_ STRAT1 STRAT2;
  CLASS RANDTRT;
  MONOTONE REG (W36 = BASE W12 W24 / DETAILS);
  MNAR ADJUST(W12 / SHIFT = <DELTA> ADJUSTOBS=(RANDTRT =
  'NARSOPLIMAB')) ;
  MNAR ADJUST(W24 / SHIFT = <DELTA> ADJUSTOBS=(RANDTRT =
  'NARSOPLIMAB')) ;
  MNAR ADJUST(W30 / SHIFT = <DELTA> ADJUSTOBS=(RANDTRT =
  'NARSOPLIMAB')) ;
  MNAR ADJUST(W36 / SHIFT = <DELTA> ADJUSTOBS=(RANDTRT =
  'NARSOPLIMAB')) ;
  VAR W12 W24 W36 BASE RANDTRT;
RUN;
```

The value of the penalty <DELTA> is progressively increased and the code re-run for each increase. This generates a series of **MI\_OUT2<DELTA>** datasets. To each of these datasets, steps 3 to 6 as described in [Appendix 1](#) will be applied, thus giving rise to a multiply imputed treatment effect estimate for each value of <DELTA> for narsoplimab vs placebo, along with its SE and CI. These treatment effect estimates and CIs will be plotted in a stacked forest plot format vs <DELTA>. The first value of <DELTA> whereby the CI includes zero will be identified as the tipping point.

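### The printed pooling code in SAP Appendix 1 (reused by Appendix 2) averages the treatment difference over Weeks 12 to 36 instead of returning the Week 36 difference

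*SAP*

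**What the plan says.** SAP 2.9.2.1 fixes the target: "The difference in least squares (LS) means at Week 36 between the treatment groups and its 95% confidence interval (CI) will be estimated". For jump-to-placebo, SAP 2.9.2.2 says: "Each of the imputed complete datasets from Step 2 will be analysed with the same MMRM model used for the primary analysis". Estimates and standard errors are then combined by Rubin's rules. The tipping-point text in the same section scales its penalties to the primary effect and treats zero penalty as matching the primary analysis.

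Appendix 1 gives the code, introduced in 2.9.2.2 with "Example SAS code of the form to perform this first sensitivity analysis is contained in" that appendix. It creates 20 imputations ("PROC MI DATA=DATAIN SEED=<VALUE> NIMPUTE=20 OUT=MI_OUT1"), stacks Weeks 12, 24, 30 and 36 as separate records (the first is "VISIT=12; CHG_BL=W12-BASE; OUTPUT"), and fits the MMRM with "LSMEANS RANDTRT*VISIT/SLICE=VISIT PDIFF DIFF ALPHA=0.05 CL". The whole difference table and the whole LS-mean table are written out. The fifth step labels the differences with "IF A THEN COMPARISON=RANDTRT||' VS '||LEFT(_RANDTRT") and labels the LS means by arm alone. The data are sorted by that label and imputation number, and the sixth step runs PROC MIANALYZE by the label. The text calls the output dataset the final result. Appendix 2 says "To each of these datasets, steps 3 to 6 as described in" Appendix 1 will be applied for each penalty.

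**The concern.** The visit disappears before pooling. PROC MIANALYZE then receives differences from four visits, and differences between one arm at one visit and the other arm at another visit, as if all were repeated imputations of a single quantity. What comes out is neither the Week 36 estimate nor a correct standard error for anything else.

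The Week 12 urine is collected between T10 and T11, during weekly dosing (Protocol 10.2.3.4). The Week 36 value is the endpoint. A sensitivity analysis that averages them no longer tests the Week 36 claim. The tipping point would also belong to a different quantity from the one whose p-value it is meant to tip. These analyses would accompany an interim result that SAP 2.9.5 says may support regulatory filings.

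**Working it through.** The plan prints no figure on this point to reproduce, so the check is a trace of the code followed by arithmetic and simulation.

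**Row count.** Two arms by four visits give 8 LS means and 8 x 7 / 2 = 28 pairwise differences per imputation. The SLICE option adds F-tests and does not filter this table. RANDTRT precedes VISIT in the CLASS statement, so every narsoplimab cell precedes every placebo cell.

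| Label | Rows per imputation |
|---|---|
| Narsoplimab vs placebo | 4 x 4 = 16 (4 same-visit, 12 cross-visit) |
| Narsoplimab vs narsoplimab | 6 |
| Placebo vs placebo | 6 |

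With 20 imputations, 16 x 20 = 320 rows enter one BY group. For a Week 36 result there should be 20.

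**Point estimate.** Write N_i and P_j for the arm means at visits i and j. The mean of N_i - P_j over all 16 pairs is mean(N) - mean(P), which equals the unweighted mean of the four same-visit differences. In single simulated trials the two agreed to four decimals. The third step subtracts baseline from values already defined as changes. Baseline is a covariate in the model, so this does not alter the arm difference.

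**Standard error.** Rubin's total variance is W + (1 + 1/m)B. Take 90 per arm and SD 0.80 (SAP 1.3.1), with an assumed within-patient correlation of 0.6 and, for this hand calculation, complete data and flat placebo.

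- W = 2 x 0.64/90 = 0.01422.
- Sampling spread of visit means adds 2 x (0.64/90) x (1 - 0.6) x 3/4 = 0.00427 to B.
- For an assumed fading profile of -0.55, -0.45, -0.35, -0.20 (mean -0.3875), the profile itself adds (0.1625² + 0.0625² + 0.0375² + 0.1875²)/4 = 0.01672 to B.

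With m = 320 the finite-sample factors are negligible. The coded SE is about sqrt(0.01422 + 0.00427 + 0.01672) = 0.188 for the fading profile and sqrt(0.01849) = 0.136 for a constant effect. The true SE of the four-visit average is sqrt(0.01422 x (1 + 3 x 0.6)/4) = 0.100. The coded SE is therefore wrong even for the average.

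**Simulation at SD 0.80.** 90 per arm, correlation 0.6, 15% monotone dropout, placebo-based sequential imputation, 20 imputations, 400 trials per profile. The model is simplified, with no covariates. Profiles are the differences at Weeks 12/24/30/36.

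| Profile | As coded: estimate; reported SE; empirical SD; rejection | Week 36 rows only: the same |
|---|---|---|
| Constant -0.393 | -0.381; 0.140; 0.097; 86.8% | -0.371; 0.125; 0.115; 87.0% |
| -0.55/-0.45/-0.35/-0.20 | -0.389; 0.185; 0.097; 61.0% | -0.218; 0.125; 0.115; 41.0% |
| -0.50/-0.35/-0.20/0 | -0.273; 0.219; 0.097; 7.0% | -0.040; 0.126; 0.115; 4.3% |
| -0.10/-0.25/-0.35/-0.393 | -0.252; 0.170; 0.097; 22.0% | -0.348; 0.125; 0.116; 79.5% |

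**Simulation at the blinded SD of 0.63.** Assumed correlation 0.7 and missingness 4/8/12/15%.

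- Fading (-0.60/-0.50/-0.40/-0.25): -0.42 (SE 0.15) as coded, -0.26 (SE 0.10) at Week 36.
- Growing to -0.43: rejection about 33% as coded, 98% at Week 36.
- Constant: same estimate, SE 0.111 as coded and 0.099 at Week 36.

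**The case against.** The code is offered as an example, and the surrounding prose points to Week 36. The primary-analysis code in 2.9.2.1 also outputs every arm-by-visit difference unfiltered, and the text then selects Week 36. The printed code needs editing before it runs at all: the REPEATED statement uses PATIENT= where PROC MIXED expects SUBJECT=, and Appendix 2 shifts Week 30 while leaving it out of its variable list. A programmer would probably notice 320 imputations, or rows comparing an arm with itself.

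Much of this stands. The conflict is between code and text; the SAP does not state an intention to average visits. But the parallel with 2.9.2.1 is incomplete. There each visit keeps its own row and the reader can pick Week 36. In Appendix 1 the visit is lost at pooling and cannot be recovered, the pooling is written out line by line, and nothing in the SAP corrects it.

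Two stronger readings are tempting. One is that the fault makes the trial look more robust than it is. The documents do not support that as a general statement: they give no visit-by-visit effect profile, a growing effect is penalised, and the reported SE was too large in every profile above. The design also allows six weeks of extended treatment after Week 12 and relapse retreatment after Weeks 24 or 30, so Week 36 is not a clean off-drug visit and fading cannot be presumed. The other reading is that type I error is inflated. These analyses have no place in the testing hierarchy of SAP 2.9.1. With no effect left at Week 36, the coded rejection rate was 7.0% against 4.3% in the table above, and other runs gave 4% to 9%.

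**Conclusion.** Wrong as written, in sensitivity analyses only. That the code pools 320 rows into a four-visit average, with an SE that is invalid for either target, follows from the code and needs no assumption beyond the arm labels shown in the appendices. The arm LS means are averaged over visits in the same way. Both jump-to-placebo and tipping-point results are affected. Even at zero penalty the tipping-point output would not target the primary contrast.

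The size and direction depend on assumed profiles, correlation and dropout. A fading effect is overstated, a growing one understated, and a constant one keeps its estimate with a larger SE. The primary MMRM, its p-value and the alpha allocation are unaffected.

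**What to change.** In the fifth step of Appendix 1, before PROC MIANALYZE, keep DIFF rows with VISIT=36 and _VISIT=36, and LSMEANS rows with VISIT=36. This leaves 20 rows per comparison and removes the within-arm differences.

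If other visits are wanted, apply VISIT=_VISIT to the DIFF rows only, because LSMEANS rows carry no _VISIT and would be dropped. Then add VISIT to both the PROC SORT and the PROC MIANALYZE BY statements. State that the Week 36 row is the sensitivity result, and carry the change into Appendix 2.

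The cost is a few lines in a SAP appendix. No new data are needed, and the primary analysis does not change. A simple programming check is that PROC MIANALYZE reports 20 imputations for each comparison.
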